### **5.6. Stopping Rules**

#### **5.6.1. Individual Virologic Stopping Rules**

Treatment will be discontinued in any subject with on-treatment virologic failure, defined as any one of the following:

- Confirmed  $1 \log_{10}$  increase in HCV RNA from post-baseline nadir
- Confirmed increase in HCV RNA  $\geq$  LLOQ in any subject who achieved HCV RNA  $<$  LLOQ

Confirmation should be performed as soon as possible after an initial HCV RNA value that may indicate virologic failure is reported.

After completion of study-related procedures in the current study, the investigator may offer an approved poststudy HCV treatment regimen consistent with local standard-of-care treatment guidelines to subjects who have on-treatment virologic failure or posttreatment virologic relapse. For those subjects who generally comply with the study protocol and experience lack of efficacy (failure to achieve SVR12 or SVR24) with the investigational regimen, the Sponsor may reimburse the investigator for the cost of a course of poststudy medication depending on local drug access and reimbursement policies.

### **5.6.2. Individual Safety Stopping Rules**

Treatment will be discontinued in any subject who experiences any one of the following:

- Confirmed elevation of ALT and/or AST  $> 5 \times$  baseline or post-baseline nadir, and  $> 5 \times$  ULN
- Confirmed elevation of ALT and/or AST  $> 15 \times$  ULN
- Confirmed elevation of ALT and/or AST  $> 3 \times$  post-baseline nadir, is  $> 3 \times$  ULN, and total bilirubin  $> 2 \times$  ULN, without any alternative causes or reason for these elevations
- Confirmed new onset  $\geq$  grade 3 elevation in creatinine or decreased GFR  $< 30 \text{ mL/min}/1.73 \text{ m}^2$
- Any SAE or grade 4 AE (including any confirmed grade 4 laboratory abnormality reported as an AE) that are considered by the investigator to be related to study drugs, *Note: To warrant treatment discontinuation, a grade 4 laboratory abnormality should have clinical findings expected to be associated with the laboratory abnormality. Subjects with isolated asymptomatic laboratory abnormalities without any clinical correlations are allowed to remain on treatment with continued monitoring according to the preference of the investigator.*
- Pregnancy during treatment (i.e., in female study subjects)

A confirmed value is defined as one that is repeated at the next subsequent test. Any of the above laboratory results and all  $\geq$  grade 3 new onset laboratory abnormalities must be repeated as soon as possible, preferably within 48 hours upon reporting of the initial value.

Additional follow-up and medical care, beyond what is specified in the protocol, is described in Section 5.6.3.

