- Alanine aminotransferase (ALT) or AST > 10 x ULN
- Total bilirubin > 3 mg/dL (> 51.3  $\mu$ mol/L)
- Albumin < 2.8 g/dL (< 28 g/L)
- International Normalized Ratio (INR) > 2.2 unless subject has a stable INR on an anticoagulant
- Hemoglobin < 10 g/dL
- Hemoglobin A1c (HbA1c) > 8.5%
- Platelet count < 50 x 10^9/L

- Estimated glomerular filtration rate (eGFR) < 30 mL/min/1.73 m^2 as estimated by the Modification of Diet in Renal Disease (MDRD) formula
- Concomitant grade  $\geq 2$  toxicity of both lipase and amylase per Division of AIDS criteria (<https://rsc.niaid.nih.gov/sites/default/files/daidsggradingcorrectedv21.pdf>)

*Note: Retests of Screening laboratory parameters or assessments may be permitted once in certain scenarios with medical monitor approval. Such scenarios may include lab processing error, results inconsistent with subject's historical values/medical history, or other extenuating circumstances such as a recent or intercurrent illness potentially affecting Screening laboratory results.*

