### **5.6.3. Study Stopping Rules**

The study will be paused in any of the following scenarios:

- If > 3 of the first 60 subjects experience (a) confirmed elevation of ALT and/or AST > 5 x baseline or post-baseline nadir, and > 5 x ULN OR (b) confirmed elevation of ALT and/or AST > 15 x ULN OR (c) any SAE or grade 4 AE which are considered by the investigator to be related to study drugs
- If > 15 subjects at any time during the trial experience (a) confirmed elevation of ALT and/or AST > 5 x baseline or post-baseline nadir, and > 5 x ULN OR (b) confirmed elevation of ALT and/or AST > 15 x ULN
- Any SAE or grade 4 AE which is considered by the investigator to be related to study drugs
- After three or more similar grade 3 or higher AEs considered by the investigator to be related to study drugs

Any of these circumstances will result in no additional subjects being enrolled. Subjects who are tolerating treatment may continue to receive study drugs. The Sponsor will collect and review all the available data with the clinical investigators and with regulatory authorities, to obtain agreement on a plan forward.

*Note: ALT/AST increases associated with virologic failure would not trigger the above stopping rules.*

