**Table 2: Schedule of Assessments**

Study Week/Day:	Screening a	Baseline	Treatment Period					Follow-up Period		
			± 1 day		± 3 days		+ 3 days	Following Last Treatment Visit; ± 5 days	Week 4	Week 12
			Week 1 Day 8	Week 2 Day 15	Week 4 Day 29	Week 6 Day 43	Week 8 Day 57 c			
Eligibility										
Informed consent	X									
Medical history	X									
Demographics	X									
Inclusion/Exclusion Criteria	X	X								
Physical Examination and Vital Signs										
Complete physical examination	X	X					X	X		
Symptom-targeted examination			X	X	X	X			X	
Vital signs	X	X	X	X	X	X	X	X		
Height (screen only) and weight	X	X			X		X	X		
Triplicate 12-lead ECG d	X	X			X		X	X	X	
Liver staging	X									
Laboratory										
Clinical labs and urinalysis	X	X	X	X	X	X	X	X		
HBV (HBsAg), HCV (anti-HCV Ab), and HIV screen; hemoglobin A 1c	X									
Pregnancy test e	X	X			X	X	X	X		
Pharmacodynamics and Pharmacokinetics										
HCV genotyping	X									
HCV RNA quantitation	X	X	X	X	X	X	X	X	X	X
Viral resistance sample f	X	X	X	X	X	X	X	X	X	X

Study Week/Day:	Screening a	Baseline	Treatment Period						Follow-up Period		
			± 1 day		± 3 days		+ 3 days	ET	Following Last Treatment Visit; ± 5 days		
			Week 1 Day 8	Week 2 Day 15	Week 4 Day 29	Week 6 Day 43			Week 4	Week 12	Week 24
PK Sample g		X	X	X	X	X	X				
Optional PK-only substudy h				Serial blood sampling at any treatment period visit as early as Week 2							
Optional PK/VK substudy h			Days 1, 2, and 3								
Study Intervention											
Study drug administration		X	At-home dosing for full treatment period (Days 1-56) unless otherwise specified								
Review compliance with study drugs i			X	X	X	X	X	X			
Adverse Event and Concomitant Medication Monitoring											
Concomitant medications i	X	X	X	X	X	X	X	X	X		
AEs i	X	X	X	X	X	X	X	X	X		
SAEs i	X	X	X	X	X	X	X	X	X	X	X

AEs = adverse events; anti-HCV Ab = anti-HCV antibody; APRI = aspartate aminotransferase (AST) to platelet ratio index; BMI = body mass index; ECG(s) = electrocardiogram(s); ET = early termination; HBsAg = Hepatitis B virus surface antigen; HBV = Hepatitis B virus; HCV = Hepatitis C virus; HIV = Human Immunodeficiency virus; PK = pharmacokinetic; SAEs = serious adverse events; VK = viral kinetics

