a Screening window may be extended to 42 days for extenuating circumstances with Sponsor approval.

b Day 1 assessments performed prior to dosing.

c The last dose is on Day 56. The last visit of the treatment period shall occur no sooner than Day 57 and no later than Day 60 (inclusive).

d Three consecutive determinations collected, with no less than 1 minute between individual ECGs. Complete ECGs prior to any blood draws.

e For females of childbearing potential, serum or urine is acceptable.

f Plasma samples collected for resistance testing. At least one baseline resistance sample is needed (Screening and/or Day 1 predose); there is no protocol deviation if there is one evaluable baseline sample for resistance testing. In addition, the resistance sample is not required for screening and eligibility purposes.

g On Day 1, the PK sample will be obtained predose. The sampling time and time of last dose must be recorded.

h See Table 3

i Subjects may be contacted between visits to assess compliance, concomitant medications, and AEs/SAEs.

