#### **6.6. Baseline Definition**

Baseline is defined as the last available assessment prior to first dose of study treatment (BEM and/or RZR).

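### The combined ALT/AST-plus-bilirubin stopping rule uses only the post-baseline nadir, so it cannot be met at the first on-treatment sample (Day 8) and leaves an ALT/AST range uncovered by the numeric rules when baseline is below 5 x ULN

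*Protocol*

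**What the plan says.** Protocol Section 5.6.2 lists the events at which a subject's treatment will be discontinued. Its first three bullets are numeric liver rules, each requiring confirmation:

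- **First bullet:** ALT and/or AST above 5 times a reference value and above 5 x ULN. The reference wording is "baseline or post-baseline nadir, and".
- **Second bullet:** ALT and/or AST above 15 x ULN.
- **Third bullet:** ALT and/or AST above 3 times a reference value and above 3 x ULN, with total bilirubin above 2 x ULN and no other explanation. The reference wording is "post-baseline nadir, is". Baseline is not named.

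On confirmation, the section says: "A confirmed value is defined as one that is repeated at the next subsequent test". The study-level pause rules in Section 5.6.3 use the first bullet's reference: "confirmed elevation of ALT and/or AST > 5 x baseline or post-baseline nadir, and > 5 x ULN". They contain no combined bilirubin criterion.

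On timing, the Table 2 row "Clinical labs and urinalysis" is marked at Screening and Baseline and then from Week 1 (Day 8). Footnote b to that table says "Day 1 assessments performed prior to dosing". SAP Section 6.6 adds: "Baseline is defined as the last available assessment prior to first dose of study treatment (BEM and/or RZR". Table 3 adds PK and viral-kinetic samples on Days 2 and 3 for substudy subjects, but no clinical laboratory tests.

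On entry, Protocol Section 4.3 excludes "Alanine aminotransferase (ALT) or AST > 10 x ULN" at Screening, so subjects may enter with values up to 10 x ULN.

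**The concern.** The third bullet is the only rule in the protocol that acts on ALT/AST and bilirubin together, and it is meant to act at a lower ALT/AST multiple than the first. Its reference value exists only once treatment has started. At the first post-baseline sample, the nadir is either undefined or is that sample itself.

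A subject whose ALT/AST and bilirubin are both raised at Day 8 therefore cannot meet the rule at the first scheduled safety check. If that value is already above baseline, it also becomes the yardstick for later visits until a lower value is recorded. What is at stake is mandatory discontinuation of a subject with a possible early liver signal. No efficacy estimate or sample size depends on it.

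**Working it through.** The plan gives no figure to reproduce here, so the check applies the three liver rules literally. All ALT/AST values are in multiples of ULN. B is baseline and x is the Day 8 value. Bilirubin is taken as above 2 x ULN, with no alternative cause and the value confirmed on repeat. The baselines are illustrative.

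**Day 8 as written**

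- First bullet: met when x > max(5B, 5).
- Second bullet: met when x > 15.
- Third bullet: nadir = x, so x / nadir = 1. The condition x > 3 × nadir is never true. If the nadir is treated as not yet defined, the result is the same. A confirmatory repeat at or below x also has a ratio of at most 1.

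The numeric rules therefore trigger at Day 8 only when x > min(max(5B, 5), 15).

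**Day 8 with baseline also a reference**

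The third bullet would be met when x > max(3B, 3). The missed range is then

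max(3B, 3) < x ≤ min(max(5B, 5), 15).

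| Baseline B | max(3B, 3) | min(max(5B, 5), 15) | Missed at Day 8 |
|---|---|---|---|
| ≤ 1 | 3 | 5 | > 3 to 5 |
| 1.5 | 4.5 | 7.5 | > 4.5 to 7.5 |
| 2 | 6 | 10 | > 6 to 10 |
| 3 | 9 | 15 | > 9 to 15 |
| 4 | 12 | 15 | > 12 to 15 |
| 4.5 | 13.5 | 15 | > 13.5 to 15 |
| ≥ 5 | ≥ 15 | 15 | none |

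The range closes exactly at B = 5, because 3 × 5 = 15 and the second bullet takes over. A grid search over x from 0.01 to 60 in steps of 0.01, with B from 0.5 to 10, gave the same limits.

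**Later visits**

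If the Day 8 value x is the only post-baseline value, the lowest Day 15 ALT/AST threshold across the three rules is:

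- as written: min(max(5·min(B, x), 5), 15, max(3x, 3));
- with baseline added: min(max(5·min(B, x), 5), 15, max(3·min(B, x), 3)).

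| B | Day 8 x | As written | With baseline added |
|---|---|---|---|
| 1 | 1.5 | > 4.5 | > 3 |
| 1 | 2 | > 5 | > 3 |
| 2 | 3 | > 9 | > 6 |
| 3 | 4 | > 12 | > 9 |
| 5 | 2 | > 6 | > 6 |

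For B from 1 to 3, the third bullet adds nothing to the first two once 3x ≥ 5B, that is x ≥ 1.67B, as long as no lower value follows. The last row shows that when ALT/AST falls on treatment the two wordings agree.

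**Persistence**

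Take B = 1, with ALT 4 and bilirubin 2.5 x ULN at Days 8, 15, 29 and 43. ALT never exceeds 5, so the first two bullets are not met. The ratio to nadir stays at 1, so the third is not met either. With baseline as a reference, 4 > 3 × 1 meets the third bullet at Day 8 and again on repeat. A slow decline of 4.5, 4.4, 4.0, 3.6, 3.2 gives the same contrast.

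**The case against.** The strongest reply is that the gap is narrow and partly backstopped.

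- **Other routes.** Section 5.6.2 also stops treatment for a related SAE or related grade 4 AE. An unexplained joint rise could be judged an important medical event, and hence an SAE, under Section 7.1. Section 5.7 lets the investigator withdraw a subject for safety at any time. The third bullet itself needs a judgement that no other cause exists, so it was never purely mechanical.
- **Narrowness.** The failure needs a baseline below 5 x ULN, an ALT/AST rise to more than 3 times baseline by Day 8, bilirubin above 2 x ULN, no alternative cause, a value inside the missed range, and no earlier lower post-baseline value. Protocol Sections 1.1, 1.2.2 and 1.4 report no concerning laboratory pattern with either drug.
- **The nadir is a sensible reference.** Where ALT/AST falls on treatment, it is equal to baseline or stricter. The documents do not say whether baseline was left out deliberately.
- **Cost.** An amendment goes to every ethics committee. An extra discontinuation may forfeit part of a potentially curative course. Under SAP Table 5, a drug-related AE discontinuation with no later RNA result counts as an SVR12 failure.

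Most of this stands as a limit on severity. The range is uncovered by the numeric rules, not by every possible route. But the other routes rest on further judgement and do not make the combined rule work at Day 8. The case for the nadir supports keeping it; it does not support leaving baseline out, since the first bullet uses both references in the same subjects.

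**Conclusion.** The concern holds. As written, the combined rule cannot be met at the first post-baseline sample. For baselines below 5 x ULN, with bilirubin above 2 x ULN, ALT/AST above max(3B, 3) and up to min(max(5B, 5), 15) x ULN triggers none of the three numeric liver rules at Day 8. A raised Day 8 value then lifts the rule's later threshold.

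This should be fixed because a mandatory safety rule fails at the first scheduled check.

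The conclusion assumes that Day 8 is the first post-baseline laboratory sample; an earlier unscheduled sample would move the same problem to that sample. It affects only subjects whose ALT/AST is already above baseline at that point. The documents give no joint ALT/AST and bilirubin distribution, so the ranges show where the gap lies and not how often a subject would fall in it.

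**What to change.** In the third bullet of Protocol Section 5.6.2, insert *baseline or* before the nadir reference, so that it matches the first bullet. State that exceeding 3 times either reference is enough, so the lower one governs. Leave the 3 x ULN, bilirubin and alternative-cause conditions as they are. The rule can then be evaluated at Day 8, keeps the stricter nadir reference when ALT/AST falls, and is never looser than now.

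No new tests are needed, because baseline ALT/AST is already collected. The cost is a protocol amendment with ethics committee submission and an occasional extra discontinuation, which may shorten a subject's course and could count against SVR12. If dosing is already complete, which the documents do not say, carry the corrected wording into the later-phase studies that this trial is meant to support.

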### **5.6.3. Study Stopping Rules**

The study will be paused in any of the following scenarios:

- If > 3 of the first 60 subjects experience (a) confirmed elevation of ALT and/or AST > 5 x baseline or post-baseline nadir, and > 5 x ULN OR (b) confirmed elevation of ALT and/or AST > 15 x ULN OR (c) any SAE or grade 4 AE which are considered by the investigator to be related to study drugs
- If > 15 subjects at any time during the trial experience (a) confirmed elevation of ALT and/or AST > 5 x baseline or post-baseline nadir, and > 5 x ULN OR (b) confirmed elevation of ALT and/or AST > 15 x ULN
- Any SAE or grade 4 AE which is considered by the investigator to be related to study drugs
- After three or more similar grade 3 or higher AEs considered by the investigator to be related to study drugs

Any of these circumstances will result in no additional subjects being enrolled. Subjects who are tolerating treatment may continue to receive study drugs. The Sponsor will collect and review all the available data with the clinical investigators and with regulatory authorities, to obtain agreement on a plan forward.

*Note: ALT/AST increases associated with virologic failure would not trigger the above stopping rules.*

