- Is an important medical event that may jeopardize the subject or may require intervention to prevent one of the other outcomes listed above (according to medical judgment of the qualified investigator)

Laboratory abnormalities without clinical significance are not recorded as AEs or SAEs. However, laboratory abnormalities that require medical or surgical intervention or lead to study drug interruption, modification, or discontinuation must be recorded as an AE, as well as an SAE, if they meet the definition above. In addition, laboratory or other abnormal assessments (eg, ECG, X-rays, vital signs) that are associated with signs and/or symptoms must be recorded as an AE or SAE if they meet the definition of an AE or SAE as described above. If the laboratory abnormality is part of a syndrome, record the syndrome or diagnosis (e.g., anemia), not the laboratory result (i.e., decreased hemoglobin). Laboratory abnormalities that do not require medical intervention or action are generally not considered AEs.

Laboratory abnormalities will be graded based on the Division of AIDS (DAIDS) Table for Grading the Severity of Adult and Pediatric Adverse Events, Version 2.1 . If a value falls within the local laboratory normal range, then it will not be graded. For AEs associated with laboratory abnormalities, the event should be graded on the basis of the clinical severity in the context of the underlying conditions; this may or may not be in agreement with the grading of the laboratory abnormality.

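### Protocol section 5.6.3 omits the ALT/AST-plus-bilirubin criterion of 5.6.2, so a single such case pauses the study only if the investigator classes it as a related SAE or grade 4 AE

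*Protocol*

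**What the plan says.** Protocol section 5.6.2 has three liver criteria that stop treatment in a subject, each confirmed on the next test:

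- ALT and/or AST above 5 x baseline or nadir, and above 5 x ULN;
- ALT and/or AST above 15 x ULN;
- ALT and/or AST above 3 x post-baseline nadir and above 3 x ULN, with total bilirubin above 2 x ULN, "without any alternative causes or reason for these elevations".

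Section 5.6.3 has four bullets that pause the study:

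- Bullet 1: "If > 3 of the first 60 subjects experience (a) confirmed elevation of ALT and/or AST > 5 x baseline or post-baseline nadir" (and above 5 x ULN), or (b) above 15 x ULN, or (c) a related SAE or grade 4 AE.
- Bullet 2: limb (a) or (b) in more than 15 subjects at any time.
- Bullet 3: "Any SAE or grade 4 AE which is considered by the investigator to be related to study drugs".
- Bullet 4: "After three or more similar grade 3 or higher AEs considered by the investigator to be related to study drugs".

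A pause stops enrolment while the sponsor reviews the data with investigators and regulators. Treatment need not stop: "Subjects who are tolerating treatment may continue to receive study drugs". SAP sections 4.1 and 5.1 refer back to the protocol's rules and add no trigger.

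On classification, protocol section 7.1 says that laboratory abnormalities that "lead to study drug interruption, modification, or discontinuation must be recorded as an AE". They are also SAEs only if they meet that definition. The important-medical-event route to an SAE is open "according to medical judgment of the qualified investigator". For AEs tied to laboratory values, "the event should be graded on the basis of the clinical severity", which may differ from the laboratory grade.

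**The concern.** Section 5.6.3 takes over the first two liver criteria of 5.6.2 almost unchanged and leaves out the third. In this reviewer's judgment, a rise in ALT/AST with bilirubin and no other explanation is the pattern that a liver-safety pause rule should most clearly cover. As written, such a case can end one subject's treatment and still reach no study-level rule, depending on how the AE is classified.

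This matters more after the lead-in. The interim safety review in section 8.7 covers only the lead-in group, which excludes cirrhosis. All cirrhotic subjects enrol among the later 220, when 5.6.3 is the only prespecified safety pause rule.

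**Working it through.** The plan gives no figure on this point to reproduce. The check compares the two rule sets and then sizes the cost of a change.

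**1. ALT/AST values that meet the combined criterion but neither limb.** Let n be the post-baseline nadir in multiples of ULN, with baseline at least n, and bilirubin above 2 x ULN. Limb (a) is read against the nadir, which gives the smallest gap. The combined ALT/AST condition holds, and limbs (a) and (b) both fail, when

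max(3n, 3) < ALT/AST ≤ min(15, max(5n, 5)).

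| Nadir (x ULN) | Band (x ULN) |
|---|---|
| up to 1 | above 3, up to 5 |
| 2 | above 6, up to 10 |
| 3 | above 9, up to 15 |
| 4 | above 12, up to 15 |
| 5 or more | none |

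Example: nadir 3.5, ALT 14, bilirubin 4. The combined criterion is met (14 > 3 x 3.5 = 10.5). Limb (a) fails (14 < 5 x 3.5 = 17.5) and limb (b) fails (14 < 15).

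**2. Routes to a pause for one combined case.**

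- Above limb (a) or (b): it counts toward more than 3 of the first 60 or more than 15 overall, but does not pause the study alone by that route.
- Inside the band: it adds nothing to limbs (a) or (b).
- In either position: bullet 3 pauses the study on this one case if the investigator calls it related and either serious or grade 4.
- Otherwise: bullet 4 applies only from the third similar related AE of grade 3 or higher.

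Having no alternative cause makes a related call likely under Table 4 of the protocol. It does not settle seriousness or grade. A confirmed, asymptomatic case recorded as a non-serious AE below grade 4 can therefore stay outside bullet 3.

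**3. How often a single-case trigger would fire.** The documents give no case rate, so p is assumed and cases are taken as independent: P(at least one) = 1 − (1 − p)^N.

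| Assumed p | N = 60 | N = 220 | N = 280 |
|---|---|---|---|
| 0.1% | 5.8% | 19.8% | 24.4% |
| 0.5% | 26.0% | 66.8% | 75.4% |
| 1% | 45.3% | 89.0% | 94.0% |

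For example, 1 − 0.999^280 = 24.4%. These are gross figures: they include cases that already pause the study under bullet 3 or another route.

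**4. Why adding the criterion to the counts would not help.** If combined cases alone had to fill the count, the binomial tail gives P(at least 4 of 60) = 0.3% at p = 1%, and P(at least 16 of 280) = 0.02% even at p = 2%.

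**5. Cirrhotic subjects.** If the 20% target in Table 1 of the protocol spans GT1a to GT4, then 75 + 40 + 40 + 75 + 25 = 255 and 0.20 x 255 = 51. That is 51/220 = 23% of those enrolled after the lead-in.

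**The case against.** The strongest reply is that single-case protection already exists. An investigator who has just stopped drug for this pattern, having found no other cause, has nearly answered the relatedness question, and the important-medical-event route to an SAE is open. This stands, and it makes the gap narrow. A reader might infer that 5.6.3 cannot pause the study on a combined case at all, or only once cases accumulate. The documents do not support that, because bullet 3 needs one event.

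Second, a new bullet would import the condition of no alternative cause, and neither document defines an adjudicator or work-up for it. This also stands. The change removes dependence on seriousness and grade only.

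Third, the gap is unsized. A reader might take the 5.8% to 94.0% range as risk that the present rules miss. It is the gross chance that the proposed trigger fires at assumed rates. The documents do not support a rate as high as 1%: protocol sections 1.2.2 and 1.4 report no consistent or clinically significant laboratory patterns with either drug. DAIDS cut-offs are not printed, so the share of cases that would be grade 3 or 4 is unknown.

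Fourth, the omission may be deliberate. Section 5.6.3 also leaves out the creatinine/GFR criterion of 5.6.2, and the SAP introduction records that Amendment 3 revised these rules after regulator feedback. The documents do not show whether this case was discussed, so it cannot be called an oversight.

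Fifth, there are other safeguards: central laboratory testing, the lead-in review, SAE reporting within 24 hours, and the sponsor's power to terminate. They make cases visible or permit action, but none is a bilirubin-based pause trigger.

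**Conclusion.** The point holds in limited form. Section 5.6.3 has no pause trigger for the combined ALT/AST-plus-bilirubin criterion. A single such case pauses the study only through the investigator's classification of it as a related SAE or grade 4 AE. The residual gap is a confirmed case that stops the subject's treatment but is recorded as non-serious and below grade 4, with fewer than three similar related AEs of grade 3 or higher. Its frequency cannot be estimated from the documents.

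This rests on reading bullet 3 as printed, as a stand-alone rule for one event. The band in the working also rests on reading limb (a) against the nadir. The change is worth making because it is cheap and concerns patient safety. The documents do not show that the study lacks liver-safety protection.

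**What to change.** Add a stand-alone bullet to protocol section 5.6.3: *Any subject meeting the confirmed ALT/AST-plus-bilirubin criterion of Section 5.6.2, whatever the seriousness or grade of the AE.* Make it a single-case trigger, to match bullet 3. Do not fold it into the counts of more than 3 of 60 or more than 15. If the omission was deliberate, a stated reason in the protocol would be the alternative.

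The cost is a protocol amendment, possibly with regulator review, and some enrolment pauses beyond those that bullet 3 already causes. At any assumed rate, the gross figures in the working are an upper limit on those extra pauses. Each pause needs review with investigators and regulators.

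Screening admits bilirubin up to 3 mg/dL. Assuming a ULN of 1.0 to 1.3 mg/dL, 2 x ULN is 2.0 to 2.6 mg/dL, so some subjects may start near or above the bilirubin limit. They would still have to meet the ALT/AST rise, the confirmation and the no-other-cause conditions.
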